#### 4.2. SECONDARY ENDPOINTS

The following endpoints related to the secondary objectives will be calculated.

- Proportion of patients achieving resolution of an OFF to an ON state within 60 minutes after study drug is administered in the clinic and maintaining the ON at 60 minutes after study drug administration (per the examiner’s subjective assessment). This endpoint will be based on the examiner’s subjective assessment. In case the assessment of turning on within 60 minutes is missing but the assessment of maintaining the ON at 60 minutes has been done, the patient will be classified based on the available assessment. In case the assessment of maintenance of ON at 60 minutes is missing, the patient will be classified as not achieving resolution of an OFF to an ON state.

## Statistical Analysis Plan

- Change from baseline (3 consecutive days prior to TV1, or in case of missing data, the last 3 recorded days before TV1) in patient-recorded total daily OFF time, assessed by the patient and recorded in the PD Diary for 3 consecutive days prior to in-clinic visits (or in case of missing data, the last 3 recorded days before the visit). The validity of the PD diary entries will be checked prior to including a diary day in the summary calculations. Only valid diary days will be included in the diary summarizations. Change from baseline in total daily ON time without dyskinesia, in total daily ON time with non-troublesome dyskinesia, and in total daily ON time with troublesome dyskinesia will be calculated similarly.
  - A day will be considered as being valid if at least 80% of the entries during the day have been completed per instructions. That is, for each half hour period, only one entry among the responses (Asleep, OFF, ON without dyskinesia, ON with non-troublesome dyskinesia, or ON with troublesome dyskinesia) has been checked. The entry will not be used if no responses are checked or more than one response is checked. However, if the proportion of entries rejected due to multiple checked responses is large, sensitivity analysis will be performed by using the worst case out of the entries that had been checked. The worst case will be defined in the following order: OFF, ON with troublesome dyskinesia, ON with non-troublesome dyskinesia, ON without dyskinesia, Asleep. In case there are duplicate entries (i.e., multiple entries recorded with same date and time interval), the worst entry will be used for the date and time interval in question. The worst entry will be selected in the order defined above.
  - All diary data will be normalized to 16 awake hours per day. The daily OFF time will be extrapolated to a 16 hour period by determining the percentage of OFF time among accurately recorded entries, excluding asleep time and missing/non-valid recordings, and by multiplying this percentage by 16 hours.
    - $\text{Off Time} / (\text{Total time recorded} - \text{Asleep Time} - \text{missing time interval}) \times 16$
  - The mean daily OFF time prior to each visit will be calculated as mean value of the valid days documented in the patient's diary prior to that visit. In case there are gaps within the 3 days preceding the visit, the last 3 recorded days before the visit will be used regardless of the gaps. If there are more than 3 valid days, only the last 3 days will be used. If there are only 1 or 2 valid days, the average of these days will be used.
- Change from TV1 (baseline) in PDQ-39 sub-scores (mobility score, activities of daily living, bodily discomfort score, emotional wellbeing score, social support score, communication score, cognitive impairment score, and stigma score) and summary

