11.2.1.2. At-Home Assessments

11.2.1.2.1. PD Diary

During the 3 consecutive days prior to SV2 and TV1 (for CVT-301-naïve and [CVT-301-009](#) patients), and TV2, TV3, TV4, TV5, and TV6, patients will record their waking ON/OFF status (time OFF, time ON without dyskinesia, time ON with non-troublesome dyskinesia, time ON with troublesome dyskinesia) and time asleep in the PD Diary (also referred to as the PD Home Diary or “Hauser diary”) ([Hauser 2000](#)).

New diaries will be distributed at each study visit, except for TV6, and patients will bring the completed diaries to the following clinic visit. Information in the diaries will be reviewed, signed, and dated by clinic staff.

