## Statistical Analysis Plan

- For the primary analysis of spirometry and selected efficacy endpoints, likelihood-based modeling approach will be used to handle incomplete data. For this purpose, Mixed Model for Repeated Measures (MMRM) will be applied (see [Section 8.1.](#))
- Sensitivity analysis for spirometry and selected explorative efficacy endpoints will be conducted using the Multiple Imputation (MI) approach, i.e. by replacing each missing value with a set of plausible values that represent the uncertainty about the right value to impute, see [Section 9.1.](#)
- For the binary explorative efficacy endpoints, sensitivity analyses will be conducted using worst case imputation, where visits with missing data are counted as non-resolved (primary method), see [Section 8.1.](#)
- For AEs, the overall incidence of TEAEs, normalized for duration of exposure will be calculated to account for the shorter follow-up time in patients who discontinue the study prematurely, see [Section 9.4.](#)

The Safety and ITT population will be used for the analysis of the primary and secondary endpoints. This population includes all patients enrolled to study CVT-301-004E who received at least 1 dose of inhaled CVT-301, regardless of whether they have post-baseline data or not for the variable in question. The patients with no post-baseline data will not contribute to the analyses performed with the MMRM approach, but they do contribute to the sensitivity analyses using the MI approach. Due to this, no additional population, like a modified ITT population including only the patients with post-baseline will be defined.

Safety data (other than the primary endpoint) will not be subjected to any imputation and will be summarized on an observed case basis.

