## Statistical Analysis Plan

impute missing values based on a sequential procedure reflecting the monotone missing data pattern. Patients with the first missing value occurring at visit at Month 1 will have their missing Month 1 value replaced by an imputed value from a regression model with baseline value, treatment group, treatment/study group and the stratification factors as explanatory variables. In the next step, patients with their Month 3 value missing will have their missing Month 3 value replaced by an imputed value from a regression mode with baseline value, treatment group, treatment/study group and stratification factors and the Month 1 value as explanatory variables. Similar procedure will be used to replace the missing values at Month 6, 9 and 12.

The imputed datasets generated with the approach described above do contain only non-missing values and are used as input in the model for the exploratory efficacy endpoint. MMRM models similar as described above will thus be run on each of the generated imputed datasets. Finally, the MIANALYZE procedure in SAS will be applied to combine the results from these several datasets to derive an overall estimate of the within-group changes.

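### The diary fallback in SAP 4.2 has no look-back limit, so read literally it can put pre-treatment or earlier-visit days into a post-baseline OFF-time value as observed data

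*SAP*

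**What the plan says.** SAP 4.2 derives daily OFF time from the diary kept on the 3 days before a visit. It gives the fallback twice. The endpoint definition allows, for post-baseline visits, "or in case of missing data, the last 3 recorded days before the visit". The averaging rule says that, where the 3 days before the visit contain gaps, "the last 3 recorded days before the visit will be used regardless of the gaps". The baseline has a parallel rule: "3 consecutive days prior to TV1, or in case of missing data, the last 3 recorded days before TV1". The next lines of the averaging rule keep only the latest 3 days if there are more than 3 valid ones, and add: "If there are only 1 or 2 valid days, the average of these days will be used".

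No maximum look-back appears in SAP 4.2, 6.3 (Missing Data) or 6.4 (Visit Windows).

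Protocol 11.2.1.2.1 schedules the diary for the 3 days before SV2 and TV1 (CVT-301-naive and 009 patients only) and before each of TV2 to TV6. It adds: "New diaries will be distributed at each study visit, except for TV6".

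For missing visit values, SAP 6.3 states that a "likelihood-based modeling approach will be used to handle incomplete data". The multiple imputation of daily OFF time in SAP 8.1 starts from Month 1: "Patients with the first missing value occurring at visit at Month 1 will have their missing Month 1 value replaced by an imputed value".

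**The concern.** Because diary days come in short blocks before visits, there are normally no spare recorded days between one block and the next. A rule that reaches back past a gap therefore either finds nothing or lands in the previous visit's block. At TV2 that block was completed before the first dose of CVT-301.

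Daily OFF time is the efficacy endpoint that gets an MMRM, a multiple-imputation sensitivity analysis and the full set of subgroup analyses. SAP 8.1 says the focus is the change within each group. A carried value enters that change directly and is labelled observed, so neither the MMRM nor the imputation can treat it as missing. Two careful programmers could also build different OFF-time datasets, each able to claim compliance with the SAP.

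**Working it through.** The documents give no figure for this rule, so there is none to reproduce. The sample size (390 enrolled, about 290 completers) is stated not to rest on formal calculation and has no bearing here.

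**How far the rule can reach.** SAP 3.8 places TV2 to TV6 at weeks 4, 12, 24, 36 and 52. The previous block is then about 4, 8, 12, 12 and 16 weeks earlier (12 - 4 = 8, 24 - 12 = 12, 36 - 24 = 12, 52 - 36 = 16). With TV6 at week 56 or 60, as in the protocol, the last step is 20 or 24 weeks.

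**One patient.** Take a CVT-301-naive patient with assumed OFF hours of 5.0, 5.5 and 6.0 on the three baseline days (mean 5.5) and 4.5, 4.0 and 5.0 on the three TV2 days (mean 4.5). Diary days are lost from the earliest TV2 day onward, and every recorded day is valid.

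| TV2 days recorded | Literal rule: days used | Mean (h) | Change (h) | Own-visit days only: mean (h) | Change (h) |
|---|---|---|---|---|---|
| 3 | 4.5, 4.0, 5.0 | 4.5 | -1.0 | 4.5 | -1.0 |
| 2 | 6.0, 4.0, 5.0 | 5.0 | -0.5 | 4.5 | -1.0 |
| 1 | 5.5, 6.0, 5.0 | 5.5 | 0.0 | 5.0 | -0.5 |
| 0 | 5.0, 5.5, 6.0 | 5.5 | 0.0 | missing | missing |

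The 0.0 in the row with one TV2 day is a coincidence of these values. The 0.0 in the last row is not: the days used are the baseline days themselves, so the change is zero whatever their values. If instead the TV3 diary is wholly missing, the literal rule repeats the TV2 value, here -1.0 h.

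**Effect on the Month 1 mean.** Let m be the share of exposed patients who attend TV2 with no diary, and assume they have the same true mean change as the others. Under the literal rule:

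reported change = true change x (1 - m)

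For a true change of -1.0 h:
- m = 5%: -1.0 x 0.95 = -0.95 h
- m = 10%: -1.0 x 0.90 = -0.90 h
- m = 15%: -1.0 x 0.85 = -0.85 h
- m = 20%: -1.0 x 0.80 = -0.80 h

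Over the 5% to 20% range, a true -0.5 h becomes -0.475 to -0.40 h, and a true -1.5 h becomes -1.425 to -1.20 h. Both m and the true change are assumptions. Partly missing diaries are not counted.

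**Who is exposed.** In the visit-mapping table of SAP 8, Month 1 for patients who took CVT-301 in study 004 is the 004 Week 4 visit, and their 004E Month 1 visit is unused. A missing 004E TV2 diary cannot alter their Month 1 value. Former 003 and 009 patients are outside the efficacy summaries (SAP 5.3). That leaves CVT-301-naive patients (including the 005 observational arm) and former 004 placebo patients. If they make up a share e of the analysed patients, the pooled result is roughly true change x (1 - e x m), which is a smaller dilution. The documents do not give e.

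**The case against.** The strongest reply is that a pool limited to each visit's own diary was intended. Several places support it:
- A new diary is issued for each visit (Protocol 11.2.1.2.1).
- The gap sentence is triggered by gaps within the 3 days, which fits scattered days in one diary better than an absent diary.
- SAP 6.4 keeps visits as recorded in the database, and its early-termination rule accepts that a scheduled diary assessment can be missing.
- The imputation in SAP 8.1 provides for a missing Month 1 value.
- Where the SAP wants to fall back on SV2 data, for the Screening ON/OFF Log in SAP 7.2, it says so.

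All of this stands. A reader might infer that the SAP definitely prescribes carry-forward; the documents do not support that. They do not settle the opposite reading either. The endpoint definition is triggered by any missing data, and the sentence on 1 or 2 valid days does not exclude a reach-back, because a recorded day can fail the 80% validity test. Missed visits and dropout would also explain the early-termination rule and the imputation of Month 1.

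The former 004 placebo patients might be taken as proof that reach-back was meant throughout. They have no scheduled diary before 004E TV1, so their baseline seems to rest on older days. That concerns baseline only, where SAP 6.2 already takes the last non-missing assessment before the first CVT-301 dose.

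It is also fair that sites telephone patients a week before each visit about the diary and collect it at the visit, which should keep wholly missing diaries uncommon among attenders.

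Finally, a reader might infer that the OFF-time formula removes missing time twice, since it subtracts the missing interval from the total time recorded. On a day with 4.5 h missing, 7 h asleep and 5 h OFF, that would give 5 / (19.5 - 7 - 4.5) x 16 = 10.0 h instead of 5 / (24 - 7 - 4.5) x 16 = 6.4 h. The sentence above the formula rules this out, because it obtains the value "by determining the percentage of OFF time among accurately recorded entries, excluding asleep time and missing/non-valid recordings". The double subtraction would also allow 12.5 / 8 x 16 = 25 h OFF in a 16-hour day. This is a matter of wording only.

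**Conclusion.** The point holds as an unresolved conflict within the SAP. Its literal words allow earlier-visit days, and at TV2 pre-treatment days, to be counted as observed; other provisions point to a per-visit pool; and no sentence decides between them.

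Under the literal reading, an exposed patient with a full baseline diary and no TV2 diary has a change of exactly 0. At 5% to 15% wholly missing, a true -1.0 h becomes -0.95 to -0.85 h among exposed patients. This rests on an assumed rate and on equal true change in patients with and without a diary. At TV2 the pull is toward no change; at later visits the earlier value is repeated, so the direction depends on the course over time.

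The rule does not carry values past dropout, since it needs a visit to count back from. The endpoint is secondary and SAP 8.1 plans no between-group inference, so the matter is modest. It is still worth closing before the data are analysed, because the within-group change is what the study sets out to describe.

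**What to change.** Add to SAP 4.2, for post-baseline visits only: *Only valid diary days recorded after the previous study visit (and after the first CVT-301 dose) are used; if there are 1 or 2 such days they are averaged; if there are none, the visit value is missing and is handled by the MMRM/MI.* Bring both existing fallback phrases for post-baseline visits into line with it.

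Leave the baseline rule unchanged. It agrees with the baseline definition in SAP 6.2. A limit there would remove the baseline of naive patients who have only pre-SV2 diary days, and apparently of former 004 placebo patients. Baseline is a covariate in the MMRM, so those patients would drop out of the model.

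Optionally, define the total time recorded in the OFF-time formula as the 24 h grid, so that missing time is plainly subtracted once.

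The cost is one added rule and, if wanted, one definition. The downside is that slightly more post-baseline visit values will be missing, which the planned MMRM and imputation are there to handle.

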## Statistical Analysis Plan

index score. The questionnaire provides scores on eight dimensions as outlined below:

- mobility (10 items, #1 to 10)
- activities of daily living (6 items, #11 to 16)
- emotional well-being (6 items, #17 to 22)
- stigma (4 items, #23 to 26)
- social support (3 items, #27 to 29)
- cognitions (4 items, #30 to 33)
- communication (3 items, #34 to 36)
- bodily discomfort (3 items, #37 to 39)

Items are scored from 0 (never) to 4 (always). Dimension scores are obtained by dividing the sum of the item scores by the maximum possible score for any given dimension and expressing this as a percentage. For example:

- mobility = (sum of scores of #1 to 10)/(4 x 10) x 100
- activities of daily living = (sum of scores of #11 to 16)/(4 x 6) x 100

For social support, if the response indicates that a patient does not have a spouse or partner for #28, social support can be calculated as [(sum of scores of #27 and 29)/(4 x 2) x 100].

A summary index is then calculated as the sum of the total score of the dimensions divided by the number of dimensions, i.e. (sum of dimension scores / 8). If any item score is missing, the relevant dimension score and the summary index will be missing.

- Change from TV1 (pre-dose) in 9-Item PHQ-9 sum score. The sum score will be calculated as the sum of the 9 individual questions. In case of 1 or more missing questions, the sum score will be set as missing.
- Change from baseline in Impact of Parkinson's OFF Episodes Patient Survey. The Impact of Parkinson's OFF episodes patient survey score will be calculated as the sum of the individual items of the Impact of Parkinson's OFF Episodes Patient Survey questionnaire. Missing individual items will not be imputed and the sum score will be missing in case of 1 or more missing items.
- The PGI-C score. The non-missing values will be categorized as improvements (much improved, improved, a little improved) or non-improvements (no change, a little worse, worse, much worse).

## Statistical Analysis Plan

- Change from TV1 (baseline) in Schwab and England (S&E) Activities of Daily Living (ADL). No further derivation will be done for the S&E scores.
- Change from TV1 (pre-dose) in the UPDRS Part 2 score. The UPDRS Part 2 score will be calculated as the sum of the individual items of the UPDRS Part 2 questionnaire (UPDRS items 5-17). Missing individual items will not be imputed and the sum score will be missing in case of 1 or more missing items.

### 4.3. SAFETY ENDPOINTS

The following endpoints related to the secondary objectives will be calculated.

- Standard safety endpoints; for definitions see Section 9 of this SAP
  - Adverse Event (AE) reports
  - Physical examination
  - Standard and orthostatic vital signs (BP, HR and RR)
  - Clinical laboratory tests (hematology, clinical chemistry, and additional laboratory parameters)
  - 12-lead ECGs (HR, PR, QRS, QT, QT interval corrected using Bazett's formula [QTcB] and QT interval corrected using Fridericia's formula [QTcF])
  - Parkinson's Disease Impulsive-Compulsive Disorders Questionnaire (QUIP)
  - Epworth Sleepiness Scale
  - Columbia-Suicide Severity Rating Scale (C-SSRS)
- Occurrence and severity of examiner-rated dyskinesia following treatment of patients experiencing an OFF episode in the clinic. The occurrence will be based on the examiner's subjective assessment and no further derivation will be performed. Among the patients with reported dyskinesia, the severity will be classified as mild, moderate, severe or missing based on the examiner's subjective assessment and no further derivation will be performed. Only observed cases will be used for this endpoint and the visits with missing data will not be included in the analysis.
- Change from TV1 (baseline) in the UPDRS Part 4 sum scores of dyskinesias (UPDRS items 32-35) and wearing-off (UPDRS items 36-39). The dyskinesia score will be calculated as the sum of the individual items 32-35 and the wearing-off score as sum of 36-39. Missing individual items will not be imputed and the sum score will be missing in case of 1 or more missing items.
- Carbon Monoxide Diffusion Capacity (DLCO) assessed over a 12 month period. Variables will include the absolute DLCO values and DLCO expressed as % of predicted value.

## Statistical Analysis Plan

- Amphetamine Withdrawal Questionnaire (AWQ) will be assessed at the clinic in an ON state at TV1 and TV6 or Early Termination (ET) or TV4, TV5 or TV6, depending on which of the visits is the next scheduled visit after the patients enrolled into sub-study. For patients who didn't enrolled into the sub-study, the AWQ will also be completed at home at 1, 3, 6, 8, 11, 14, 17, 24, and 28 days after TV6/ET. For patients who enrolled into the sub-study, the AWQ will be assessed at home at 1, 3, 6, 8, 11, 14, 17, 24, and 28 days after TV4, TV5 or TV6, depending on which of the visits is the next scheduled visit for those patients. The total score will be calculated as the sum of the individual items 1 to 10. Missing individual items will not be imputed and the sum score will be missing in case of 1 or more missing items.
- Dopamine Dysregulation Syndrome - Patient and Caregiver Inventory (DDS-PC) will be assessed at the clinic in an ON state at TV1 and TV6 or Termination (ET) or TV4, TV5 or TV6, depending on which of the visits is the next scheduled visit after the patients enrolled into sub-study. For patients who didn't enrolled into the sub-study, the DDS-PC will also be completed at home at 1, 3, 6, 8, 11, 14, 17, 24, and 28 days after TV6/ET. For patients who enrolled into the sub-study, the DDS-PC will be assessed at home at 1, 3, 6, 8, 11, 14, 17, 24, and 28 days after TV4, TV5 or TV6, depending on which of the visits is the next scheduled visit for those patients. The total score will be calculated as the sum of the individual items 1 to 45. The below score will be used for each individual item: 0 = Not at all, 1 = Very little, 2 = A little, 3 = Quite a lot, 4 = Very much. Missing individual items will not be imputed and the sum score will be missing in case of 1 or more missing items.
- Movement Disorder Society - Unified Parkinson's Disease Rating Scale (MDS-UPDRS) Parts 1B and 2 will be assessed during drug withdrawal period. For patients who didn't enrolled into the sub-study, the MDS-UPDRS will be completed at home at 1, 3, 6, 8, 11, 14, 17, 24, and 28 days after TV6/ET. For patients who enrolled in the sub-study, the MDS-UPDRS will be assessed at home at 1, 3, 6, 8, 11, 14, 17, 24, and 28 days after TV4, TV5 or TV6, depending on which of the visits is the next scheduled visit for those patients. The Part 1B score will be calculated as the sum of the individual items 1.7 to 1.13 and the Part 2 score as sum of 2.1 to 2.13. Missing individual items will not be imputed and the sum score will be missing in case of 1 or more missing items.

## Statistical Analysis Plan

### 5. ANALYSIS SETS

#### 5.1. ALL AVAILABLE POPULATION (AAP)

The AAP will include all patients who have consented for the study, including screening failures. Unless specified otherwise, the AAP will be used for patient listings and for the summary of patient disposition.

#### 5.2. SAFETY POPULATION

The Safety Population will include all patients in AAP who are enrolled in CVT-301-004E and received at least 1 dose of inhaled CVT-301. Patients will be analysed according to the highest dose level that they received. The Safety Population will be used for all analyses of safety endpoints and summaries of patient demographics and baseline characteristics.

